9.4.3. Safety Analysis

All safety analyses will be performed on the safety analysis set. All ADEs will be summarized by each inhaler. Listings will be presented for SAEs and SADEs.

Deaths, SADEs and SAEs, if applicable, will be documented in case narrative format.

9.5. Interim Analysis

No interim analyses are planned for this study.

10. SUPPORTING DOCUMENTATION AND OPERATIONAL CONSIDERATIONS

10.1. Appendix 1: Regulatory, Ethical, and Study Oversight Considerations

10.1.1. Regulatory and Ethical Considerations

- This study will be conducted in accordance with the protocol and with:
 - Consensus ethical principles derived from international guidelines including the Declaration of Helsinki and Council for International Organizations of Medical Sciences (CIOMS) International Ethical Guidelines
 - Applicable ICH Good Clinical Practice (GCP) Guidelines and ISO 14155 2020 guidelines
 - Applicable laws and regulations
- The protocol, protocol amendments, ICF, IB and other relevant documents (e.g., advertisements) must be submitted to an IRB/IEC by the investigator and reviewed and approved by the IRB/IEC before the study is initiated.
- Any amendments to the protocol will require IEC/IRB approval before implementation of changes made to the study design, except for changes necessary to eliminate an immediate hazard to study participants.
- Protocols and any substantial amendments to the protocol will require Central Ethics Committee (CEC) approval prior to initiation except for changes necessary to eliminate an immediate hazard to study participants.
- The investigator will be responsible for the following:
 - Providing written summaries of the status of the study to the IRB/IEC annually or more frequently in accordance with the requirements, policies, and procedures established by the IRB/EC
 - Notifying the IRB/IEC of SAE or other significant safety findings as required by IRB/IEC procedures
 - Providing oversight of the conduct of the study at the site and adherence to requirements of 21 CFR, ICH guidelines, the IRB/IEC, European regulation 536/2014 for clinical studies (if applicable), European Medical Device Regulation 2017/745 for clinical device research, and all other applicable local regulations

10.1.2. Financial Disclosure

Investigators and sub-investigators will provide the sponsor with sufficient, accurate financial information as requested to allow the sponsor to submit complete and accurate financial certification or disclosure statements to the appropriate regulatory authorities. Investigators are responsible for providing information on financial interests during the course of the study and for 1 year after completion of the study.

10.1.3. Informed Consent Process

- The investigator or his/her representative will explain the nature of the study to the participant and answer all questions regarding the study.
- Participants must be informed that their participation is voluntary. Participants will be required to sign a statement of informed consent that meets the requirements of 21 CFR 50, local regulations, ICH guidelines, ISO 14155 Health Insurance Portability and Accountability Act (HIPAA), GDPR requirements, where applicable, and the IRB/IEC or study center.
- The medical record must include a statement that written informed consent was obtained before the participant was enrolled in the study and the date the written consent was obtained. The authorized person obtaining the informed consent must also sign the ICF.
- Participants must be re-consented to the most current version of the ICF(s) during their participation in the study.

A copy of the ICF(s) must be provided to the participant

A participant who is rescreened is not required to sign another ICF if the rescreening occurs within (30) days from the previous ICF signature date.

GSK (alone or working with others) may use participant's coded study data and other information to carry out this study; understand the results of this study; learn more about the study disease; publish the results of these research efforts

10.1.4. Data Protection

- Participants will be assigned a unique identifier by the sponsor. Any participant records or datasets that are transferred to the sponsor will contain the identifier only; participant names or any information which would make the participant identifiable will not be transferred.
- The participant must be informed that his/her personal study-related data will be used by the sponsor in accordance with local data protection law. The level of disclosure must also be explained to the participant who will be required to give consent for their data to be used as described in the informed consent.
- The participant must be informed that his/her medical records may be examined by Clinical Quality Assurance auditors or other authorized personnel appointed by the sponsor, by appropriate IRB/IEC members, and by inspectors from regulatory authorities.

- Where required by applicable regulatory requirements, an investigator signatory will be identified for the approval of the clinical study report. The investigator will be provided reasonable access to statistical tables, figures, and relevant reports and will have the opportunity to review the complete study results at a GSK site or other mutually-agreeable location.
- GSK will also provide all investigators who participated in the study with a summary of the study results and will tell the investigators what treatment their patients' received. The investigators are encouraged to share the summary results with the study participants, as appropriate.
- Under the framework of the SHARE initiative, GSK intends to make anonymized participant-level data from this trial available to external researchers for scientific analyses or to conduct further research that can help advance medical science or improve patient care. This helps ensure the data provided by trial participants are used to maximum effect in the creation of knowledge and understanding. Requests for access may be made through www.clinicalstudydatarequest.com.
- The procedures and timing for public disclosure of the protocol and results summary and for development of a manuscript for publication for this study will be in accordance with GSK Policy.
- GSK intends to make anonymized patient-level data from this trial available to external researchers for scientific analyses or to conduct further research that can help advance medical science or improve patient care. This helps ensure the data provided by trial participants are used to maximum effect in the creation of knowledge and understanding

10.1.5. Data Quality Assurance

- All participant data relating to the study will be recorded on printed or electronic CRF unless transmitted to the sponsor or designee electronically (e.g., laboratory data). The investigator is responsible for verifying that data entries are accurate and correct by physically or electronically signing the CRF.
- Guidance on completion of CRFs will be provided in eCRF completion guidelines.
- Quality tolerance limits (QTLs) will be pre-defined in the QTL plan to identify systematic issues that can impact participant safety and/or reliability of study results. These pre-defined parameters will be monitored during and at the end of the study and all deviations from the QTLs and remedial actions taken will be summarized in the clinical study report.
- The investigator must permit study-related monitoring, audits, IRB/IEC review, and regulatory agency inspections and provide direct access to source data documents.
- Monitoring details describing strategy including definition of study critical data items and processes (e.g., risk-based initiatives in operations and quality such as Risk Management and Mitigation Strategies and Analytical Risk-Based Monitoring), methods, responsibilities and requirements, including handling of

noncompliance issues and monitoring techniques (central, remote, or on-site monitoring) are provided in the Monitoring Plan.

- The sponsor or designee is responsible for the data management of this study including quality checking of the data.
- The sponsor assumes accountability for actions delegated to other individuals (e.g., Contract Research Organizations).
- Records and documents, including signed ICF, pertaining to the conduct of this study must be retained by the investigator for 25 years from the issue of the final Clinical Study Report (CSR)/ equivalent summary unless local regulations or institutional policies require a longer retention period. No records may be destroyed during the retention period without the written approval of the sponsor. No records may be transferred to another location or party without written notification to the sponsor.

10.1.6. Source Documents

- Source documents provide evidence for the existence of the participant and substantiate the integrity of the data collected. Source documents are filed at the investigator's site.
- Data reported on the CRF or entered in the eCRF that are transcribed from source documents must be consistent with the source documents or the discrepancies must be explained. The investigator may need to request previous medical records or transfer records, depending on the study. Also, current medical records must be available.
- Definition of what constitutes source data and its origin can be found in [Source Data Acknowledgment].
- The investigator must maintain accurate documentation (source data) that supports the information entered in the CRF.
- Study monitors will perform ongoing source data verification to confirm that data entered into the CRF by authorized site personnel are accurate, complete, and verifiable from source documents; that the safety and rights of participants are being protected; and that the study is being conducted in accordance with the currently approved protocol and any other study agreements, ICH GCP, and all applicable regulatory requirements.

10.1.7. Study and Site Start and Closure

First Act of Recruitment

The study start date is the date on which the clinical study will be open for recruitment of participants.

Study/Site Termination

GSK or designee reserves the right to close the study site or terminate the study at any time for any reason at the sole discretion of GSK. Study sites will be closed upon study completion. A study site is considered closed when all required documents and study supplies have been collected and a study-site closure visit has been performed.

The investigator may initiate study-site closure at any time, provided there is reasonable cause and sufficient notice is given in advance of the intended termination.

Reasons for the early closure of a study site by the sponsor or investigator may include but are not limited to:

For study termination:

- Discontinuation of further study intervention development

For site termination:

- Failure of the investigator to comply with the protocol, the requirements of the IRB/IEC or local health authorities, the sponsor's procedures, or GCP guidelines
- Inadequate or no recruitment of participants (evaluated after a reasonable amount of time) by the investigator
- If the study is prematurely terminated or suspended, the sponsor shall promptly inform the investigators, the IECs/IRBs, the regulatory authorities, and any contract research organization(s) used in the study of the reason for termination or suspension, as specified by the applicable regulatory requirements. The investigator shall promptly inform the participant and should assure appropriate participant therapy and/or follow-up

10.1.8. Publication Policy

- The results of this study may be published or presented at scientific meetings. If this is foreseen, the investigator agrees to submit all manuscripts or abstracts to the sponsor before submission. This allows the sponsor to protect proprietary information and to provide comments.
- The sponsor will comply with the requirements for publication of study results. In accordance with standard editorial and ethical practice, the sponsor will generally support publication of multicenter studies only in their entirety and not as individual site data. In this case, a coordinating investigator will be designated by mutual agreement.
- Authorship will be determined by mutual agreement and in line with International Committee of Medical Journal Editors authorship requirements.

10.2. Appendix 2: AEs and SAEs: Definitions and Procedures for Recording, Evaluating, Follow-up, and Reporting

10.2.1. Definition of AE

AE Definition

 • AEs are defined below, however only AEs which meet the seriousness criteria (see Section 10.2.2) will be collected in this study: • An AE is any untoward medical occurrence in a clinical study participant, temporally associated with the use of a study intervention, whether or not considered related to the study intervention. • NOTE: An AE can therefore be any unfavorable and unintended sign (including an abnormal laboratory finding), symptom, or disease (new or exacerbated) temporally associated with the use of a study intervention.

10.2.2. Definition of SAE

An SAE is defined as any serious adverse event that, at any dose:

a. Results in death
 
b. Is life-threatening The term 'life-threatening' in the definition of 'serious' refers to an event in which the participant was at risk of death at the time of the event. It does not refer to an event, which hypothetically might have caused death, if it were more severe.

c. Requires inpatient hospitalization or prolongation of existing hospitalization
 
 • In general, hospitalization signifies that the participant has been admitted (usually involving at least an overnight stay) at the hospital or emergency ward for observation and/or treatment that would not have been appropriate in the physician's office or outpatient setting. Complications that occur during hospitalization are AE. If a complication prolongs hospitalization or fulfills any other serious criteria, the event is serious. When in doubt as to whether "hospitalization" occurred or was necessary, the AE should be considered serious. • Hospitalization for elective treatment of a pre-existing condition that did not worsen from baseline is not considered an AE.

d. Results in persistent or significant disability/incapacity
 
 • The term disability means a substantial disruption of a person's ability to conduct normal life functions.

 This definition is not intended to include experiences of relatively minor medical significance such as uncomplicated headache, nausea, vomiting, diarrhea, influenza, and accidental trauma (e.g. sprained ankle) which may interfere with or prevent everyday life functions but do not constitute a substantial disruption.
e. Is a congenital anomaly/birth defect
f. Is a suspected transmission of any infectious agent via an authorised medicinal product
g. Other situations: 
 Possible Hy's Law case: $ALT \geq 3 \times ULN$ AND total bilirubin $\geq 2 \times ULN$ ($> 35\%$ direct bilirubin) or international normalized ratio (INR) > 1.5 must be reported as SAE Medical or scientific judgment should be exercised by the investigator in deciding whether SAE reporting is appropriate in other situations such as significant medical events that may jeopardize the participant or may require medical or surgical intervention to prevent one of the other outcomes listed in the above definition. These events should usually be considered serious. 
 Examples of such events include invasive or malignant cancers, intensive treatment for allergic bronchospasm, blood dyscrasias, convulsions, or development of intervention dependency or intervention abuse.

10.2.3. Definition of Cardiovascular Events

Cardiovascular Events (CV) Definition:
Investigators will be required to fill out the specific CV event page of the CRF for the following SAEs:

- Myocardial infarction/unstable angina
- Congestive heart failure
- Arrhythmias
- Valvulopathy
- Pulmonary hypertension
- Cerebrovascular events/stroke and transient ischemic attack
- Peripheral arterial thromboembolism
- Deep venous thrombosis/pulmonary embolism
- Revascularization

10.2.4. Recording and Follow-Up of SAE

SAE Recording

When an SAE occurs, it is the responsibility of the investigator to review all documentation (e.g. hospital progress notes, laboratory, and diagnostics reports) related to the event.The investigator will then record all relevant SAE information.It is not acceptable for the investigator to send photocopies of the participant's medical records to GSK in lieu of completion of the GSK required form.There may be instances when copies of medical records for certain cases are requested by GSK. In this case, all participant identifiers, with the exception of the participant number, will be redacted on the copies of the medical records before submission to GSK.The investigator will attempt to establish a diagnosis of the event based on signs, symptoms, and/or other clinical information. Whenever possible, the diagnosis (not the individual signs/symptoms) will be documented as the SAE.
Assessment of Intensity

The investigator will make an assessment of intensity for each SAE reported during the study and assign it to 1 of the following categories:
 
Mild: An event that is easily tolerated by the participant, causing minimal discomfort and not interfering with everyday activities.Moderate: An event that causes sufficient discomfort and interferes with normal everyday activities.Severe: An event that prevents normal everyday activities.An event is defined as 'serious' when it meets at least 1 of the predefined outcomes as described in the definition of an SAE, NOT when it is rated as severe.

Assessment of Causality

The investigator is obligated to assess the relationship between study intervention and each occurrence of each SAE.A "reasonable possibility" of a relationship conveys that there are facts, evidence, and/or arguments to suggest a causal relationship, rather than a relationship cannot be ruled out.The investigator will use clinical judgment to determine the relationship.Alternative causes, such as underlying disease(s), concomitant therapy, and other risk factors, as well as the temporal relationship of the event to study intervention administration will be considered and investigated.

- The investigator will also consult the Investigator's Brochure (IB) and/or Product Information, for marketed products, in his/her assessment.
- For each SAE, the investigator **must** document in the medical notes that he/she has reviewed the SAE and has provided an assessment of causality.
- There may be situations in which an SAE has occurred and the investigator has minimal information to include in the initial report to GSK. However, **it is very important that the investigator always make an assessment of causality for every event before the initial transmission of the SAE data to GSK.**
- The investigator may change his/her opinion of causality in light of follow-up information and send an SAE follow-up report with the updated causality assessment.
- The causality assessment is one of the criteria used when determining regulatory reporting requirements.

Follow-up of SAE

- The investigator is obligated to perform or arrange for the conduct of supplemental measurements and/or evaluations as medically indicated or as requested by GSK to elucidate the nature and/or causality of the SAE as fully as possible. This may include additional laboratory tests or investigations, histopathological examinations, or consultation with other health care professionals.
- If a participant dies during participation in the study or during a recognized follow-up period, the investigator will provide GSK with a copy of any post-mortem findings including histopathology.
- New or updated information will be recorded in the originally submitted documents.
- The investigator will submit any updated SAE data to GSK within 24 hours of receipt of the information.

10.2.5. Reporting of SAE to GSK

SAE Reporting to GSK via Electronic Data Collection Tool

- The primary mechanism for reporting SAE to GSK will be the electronic data collection tool.
- If the electronic system is unavailable, then the site will use the paper SAE data collection tool (see next section) to report the event within 24 hours.
- The site will enter the SAE data into the electronic system as soon as it becomes available.
- The investigator or medically-qualified sub-investigator must show evidence within the eCRF (e.g., check review box, signature, etc.) of review and verification of the

relationship of each SAE to IP/study participation (causality) within 72 hours of SAE entry into the eCRF.

- After the study is completed at a given site, the electronic data collection tool will be taken off-line to prevent the entry of new data or changes to existing data.
- If a site receives a report of a new SAE from a study participant or receives updated data on a previously reported SAE after the electronic data collection tool has been taken off-line, then the site can report this information on a paper SAE form (see next section) or to the medical monitor/SAE coordinator by telephone.
- Contacts for SAE reporting can be found in the study reference manual .

SAE Reporting to GSK via Paper Data Collection Tool

- Facsimile transmission of the SAE paper data collection tool is the preferred method to transmit this information to the medical monitor or the SAE coordinator.
- In rare circumstances and in the absence of facsimile equipment, notification by telephone is acceptable with a copy of the SAE data collection tool sent by overnight mail or courier service.
- Initial notification via telephone does not replace the need for the investigator to complete and sign the SAE data collection tool within the designated reporting time frames.
- Contacts for SAE reporting can be found in the study reference manual.

10.3. Appendix 3 CRITICAL ERROR CHECKLISTS

A critical error is defined as an error that is most likely to result in no or significantly reduced medication being inhaled. These errors will be captured in a checklist provided for HCP assessment of DPI use.

Please note, the critical error checklists are designed to record any errors that are made by the participant based on the patient information leaflet for each device. Any inadequacies of the medical devices that fall under the definition of a device deficiency (as defined in Section 10.7 Appendix 7) , must be reported separately as per Regulation (EU) 2017/745 Medical Device Regulation (MDR) Article 80(2).

10.3.1. ELLIPTA Critical Error Checklist

Protocol Identifier	Participant Identifier	ELLIPTA Checklist						
213306	

 	 	 	 	 	 	

							Visit 1

Date of Assessment:	

 	 	

			

 	 	 	

				

 	 	

		
DAY	MONTH	YEAR								
Attempt Number:	PIL (1)	HCP (2)	HCP (3)	HCP(4)						

PIL Step	PIL Wording	Error (Underlined text indicates a critical error)	Step Performed correctly	Step Performed Incorrectly
1	Prepare a dose Wait to open the cover until you are ready to take your dose. Do not shake the inhaler. • Slide the cover down until you hear a “click”.	Failed to open cover until click is heard		
		Intentionally shook the inhaler after dose preparation		
2	Inhale your medicine • While holding the inhaler away from your mouth, breathe out as far as is comfortable. Do not breathe out into the inhaler.	No exhalation before an inhalation		
		Exhaled directly into mouthpiece		

	
 Put the mouthpiece between your lips and close your lips firmly around it. Do not block the air vent with your fingers. Take one long, steady, deep breath in. Hold this breath for as long as possible (at least 3-4 seconds). Remove the inhaler from your mouth. Breathe out slowly and gently. 	No seal created by lips around the mouthpiece during the inhalation		
		Inhalation manoeuvre was NOT :		
		- long		
		- steady		
- deep				
3	Close the inhaler and rinse your mouth.	Blocked air inlet during inhalation manoeuvre		
		Did not hold breath		

Other comments:
				

[figure not shown]

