2.2. Background

The importance of correct use of inhalers is emphasised by GINA for asthma patients [GINA, 2020] and by GOLD for patients with chronic obstructive pulmonary disease (COPD) [GOLD, 2020] by ensuring selection of the appropriate inhaler, demonstration of the inhaler and assessment of inhaler use is reviewed prior to escalating therapy. Errors made by the patient can affect the amount of medication received and disease control so it is essential to ensure good inhaler technique.

Comparison of inhaler techniques between asthma and COPD patients suggests inconsistencies with some observational studies demonstrating similar error rates [Arora, 2014; Chorão, 2014; Takaku, 2017; Ocakli, 2018] and other studies demonstrating higher rates in COPD patients [Khassawneh, 2008; Melani, 2011] but when adjusting for age, inhaler and level of instruction, this difference disappeared [Melani, 2011]. Study designs often observational, in usual practice with patients being familiar with their

inhalers, in different geographical and socio-economic areas may account for the inconsistent effects. Old age [Arora, 2014; Chorão, 2014], lower socio-economic [Arora, 2014] and educational levels [Arora, 2014; Chorão, 2014] and female gender [Chorão, 2014] were risk factors for greater errors in inhaler handling.

The ELLIPTA DPI was developed to deliver various inhaled maintenance medications, including mono, dual and triple therapies, for the treatment of asthma and COPD. Participants with asthma or COPD make fewer critical errors (defined as an error that is most likely to result in no or significantly reduced medication being inhaled) and overall errors (any error in inhaler technique) with the ELLIPTA DPI than with other DPIs [van der Palen, 2016]. Furthermore, participant preference for the ELLIPTA DPI has been demonstrated previously versus other DPIs for many attributes, including ease of use and time to train [van der Palen, 2016]. The BREEZHALER DPI is also approved for use with a variety of inhaled mono- or combination-medications although has not yet been widely used by asthma patients.

The present study involves the use of ELLIPTA and BREEZHALER DPI inhalers that contain placebo and not active treatments. Participants will continue to take their own prescribed asthma medication and other concomitant medication during the study. Participants should also follow-up with their regular physician for their asthma healthcare during the study.

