8.1.1. Assessment of errors in use of inhalers

- Participants will be randomized to the order of inhaler as detailed in [Table 1](#) and the sequence of questionnaire completion is indicated in the study Schema in Section 1.2. Participants will be provided with the relevant sections of the PIL, explaining the correct use for both inhalers. The critical and overall errors per inhaler and how these have been defined are outlined in [Section 10.3 Appendix 3](#)
- The errors listed will be aligned with the correct use information from the respective PILs, in a checklist for each inhaler which will be provided to the HCPs for scoring errors during the study conduct. The checklists to be completed by the investigator will be provided.

The steps required to assess participant errors in using the inhalers is illustrated in [Figure 1](#) and summarized below:

- Participants will demonstrate inhaler use after reading the use sections of the PIL which is provided to them by the investigator (Attempt 1).
- If the participant makes any errors according to the error checklists in [Appendix 3](#), the investigator demonstrates the correct use of the inhaler, and the participant will try inhaler use again (Attempt 2). If after the first demonstration the participant continues to make errors, the investigator will again demonstrate correct inhaler use to the participant prior to the participant trying again (Attempt 3). If the participant has still not demonstrated correct use, the HCP will again demonstrate correct use for the final time, followed by the final attempt for the participant to demonstrate use of the inhaler (Attempt 4).
- Following each attempted use of the inhaler by the participant, the trained investigator will assess for, and document, any critical errors (i.e., defined as an error that is most likely to result in no or significantly reduced medication being inhaled) and non-critical errors made by the participant.
- This process of error assessment will be used to assess for critical and non-critical errors made by the participant for both inhalers being tested.
- Participants will be permitted up to a 30-minute break between completing the assessment of the first inhaler and commencing error assessments for the second inhaler.

Figure 1 Assessment of errors for each inhaler

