		Exhaled directly into mouthpiece		
8	
Inhale medicine deeply
 
Put the mouthpiece between your lips, and close your lips firmly around it.
 
Do not press the side buttons
 
 Take in one rapid and deep breath, sufficient to hear or feel the capsule. 	No seal created by the lips round the mouthpiece during inhalation		
		Pressed the side buttons while inhaling through the mouthpiece		
		Inhalation maneuver was not: -Rapid -Deep		
9	
As you breathe, the capsule should make a whirring noise
 
 If there is no whirring noise, loosen the capsule by tapping the base of inhaler and repeat step 7 and 8. 	Capsule did not whirr		
10	
Hold this breath for up to 5 secs
 
 Remove the inhaler from your mouth. 	Failed to hold breath		
11	
Check capsule chamber is empty
 
Open the capsule to check it is empty
 
If powder remains in capsule, close the inhaler and repeat steps 7-12
	Did not check the capsule chamber		
		Failed to repeat inhalation when powder remained in the capsule		
12	Close the inhaler and replace the cap	Did not close the inhaler and close the cap		
Other comments:				

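### As printed, failing to close the device is a listed non-critical error for BREEZHALER but not for ELLIPTA, which can move secondary endpoints in ELLIPTA's favour

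*Protocol*

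**What the plan says.** Protocol Section 8.1.1 states: "The errors listed will be aligned with the correct use information from the respective PILs". Section 10.3 goes further and says that "the critical error checklists are designed to record any errors that are made by the participant based on the patient information leaflet for each device".

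The last leaflet step on each form, and the errors printed beside it, are:

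| | Leaflet wording | Error(s) printed beside it |
|---|---|---|
| ELLIPTA step 3 (Section 10.3.1) | "Close the inhaler and rinse your mouth" | "Blocked air inlet during inhalation manoeuvre"; "Did not hold breath" |
| BREEZHALER step 12 (Section 10.3.2) | "Close the inhaler and replace the cap" | "Did not close the inhaler and close the cap" |

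Section 2.2 treats any fault in technique as an overall error. Under Section 8.1.1, any error on the Appendix 3 checklist leads to instruction by the HCP and a further attempt. Neither document explains why closing is treated differently on the two forms, and neither plans an analysis without the closing item.

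**The concern.** Some rows rightly exist for one device only. Capsule handling and piercing, for example, have no ELLIPTA counterpart. Closing the device is different because it appears in both leaflets.

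Take a participant who does everything else correctly but leaves both devices open. As the forms read, the ELLIPTA attempt is correct: T1 counts as an event and T2 is zero (SAP 4.3.1.5). The BREEZHALER attempt is an overall error: T1 is censored, instruction is given and T2 accrues. The same behaviour therefore counts against one inhaler only, in five places:

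- at least one overall error (SAP 4.3.1.3);
- need for further instruction (SAP 4.3.1.4);
- T1 censoring, T2 and T1+T2 (SAP 4.3.1.5);
- the number of overall errors (SAP 4.3.2.2);
- overall errors at Attempts 2 to 4, where a participant who received no instruction is set to zero errors.

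The comparative endpoints among these are each tested at the two-sided 5% level without multiplicity adjustment (SAP 2.1 and 4.3.1), in an open-label comparison of the sponsor's device with a competitor's.

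**Working it through.** **1. Is there an ELLIPTA closing error under another step?** The printed ELLIPTA errors are: cover not opened to the click; shaking; no exhalation; exhaling into the mouthpiece; no lip seal; inhalation not long, steady or deep; blocked air inlet; no breath hold. The first two belong to step 1 and the rest to step 2. The two printed beside step 3 answer step 2 instructions (keep the air vent clear, hold the breath). None concerns closing.

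**2. Is the primary endpoint touched?** Underlining marks critical errors. The step 12 error is not underlined, while several neighbouring BREEZHALER rows are, so it reads as non-critical. The sample size was set on critical errors and reproduces from Protocol 9.2 (odds ratio 0.3, SD 2.785 on the log scale, two-sided 5%, 90% power):

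n per sequence = (1.960 + 1.282)² × 2.785² / (ln 0.3)² = 10.51 × 7.756 / 1.450 = 56.2, rounded up to 57; total 2 × 57 = 114.

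Nothing in that calculation depends on the closing item.

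**3. How large could the effect be?** The documents give no rate for overall errors or for failing to close, so both are assumed here:

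- p = probability of any other listed error, equal on both inhalers;
- c = probability of failing to close, equal on both inhalers and independent of other errors;
- periods independent (Protocol 9.2 assumes no correlation between periods), n = 114, and an exact McNemar test standing in for the planned exact conditional logistic model with period.

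ELLIPTA is scored p. BREEZHALER is scored b = 1 − (1 − p)(1 − c). The discordant probabilities are p(1 − b) for ELLIPTA only and b(1 − p) for BREEZHALER only. Their ratio is the conditional odds ratio, which simplifies to

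OR = p(1 − c) / [p + c(1 − p)].

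Example with p = 0.40 and c = 0.20: b = 0.52; ELLIPTA only 0.40 × 0.48 = 0.192; BREEZHALER only 0.52 × 0.60 = 0.312; OR = 0.62.

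Odds ratio, with the probability of a two-sided p ≤ 0.05 in brackets, when true performance is equal:

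| p | c = 2% | c = 5% | c = 10% | c = 20% |
|---|---|---|---|---|
| 10% | 0.83 (4.5%) | 0.66 (12.6%) | 0.47 (40.7%) | 0.29 (92.0%) |
| 30% | 0.94 (4.1%) | 0.85 (6.8%) | 0.73 (16.6%) | 0.55 (53.9%) |
| 40% | 0.95 (4.0%) | 0.88 (5.7%) | 0.78 (12.1%) | 0.62 (39.2%) |
| 50% | 0.96 (3.9%) | 0.91 (5.1%) | 0.82 (9.4%) | 0.67 (28.3%) |

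Two further points with common errors: p = 60%, c = 5% gives 0.92 (4.6%); p = 80%, c = 10% gives 0.88 (4.6%).

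If closing is scored on both inhalers or on neither, the odds ratio is 1.00. Rejection is then 3.7% at p = 40%, and 3.0% to 3.7% for p of 10% to 50%; it is below 5% because the exact test is conservative.

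For any c > 0 the formula gives OR < 1, because the numerator shrinks and the denominator grows. The direction of this item is therefore fixed, while its size is not.

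**The case against.** The strongest objection is that the point rests on a row being absent from a table that did not survive extraction intact. Step 2 errors are printed beside step 3, and a figure is missing after the table, so a step 3 row could have been lost. The BREEZHALER step 12 row shows no tick boxes, which suggests that its layout also suffered. This stands, and it is why the first action is to look at the source form. Against it, every tick-box pair on the ELLIPTA form has a label and no stray boxes hint at a lost row.

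Second, alignment with the leaflet does not promise one row per instruction. Mouth rinsing (ELLIPTA) and tapping the base to loosen the capsule (BREEZHALER) have no row either. That is fair as a reading of Section 8.1.1. The statement in Section 10.3 that any leaflet-based error is recorded is harder to reconcile with the gap.

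Third, the two omissions are not identical. BREEZHALER step 12 combines closing with replacing a removed cap, so equal failure rates are an assumption.

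Fourth, a reader might infer that the whole overall-error comparison is tilted towards ELLIPTA. One row does not support that. The ELLIPTA manoeuvre item lists three possible failures against two for BREEZHALER, and BREEZHALER step 6 is worded so that two failures must occur together. Only the direction of the closing item is established.

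**Conclusion.** On the text available, the forms treat the same leaflet action differently, contrary to the stated purpose in Section 10.3. The consequence is confined to secondary endpoints, where this item can only favour ELLIPTA. For the yes/no endpoints it matters only when closing is the sole error in an attempt.

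At a 40% rate of other errors, the spurious odds ratio runs from about 0.95 (2% closing failure, 4.0% rejection) to 0.62 (20%, 39% rejection). It is negligible when closing failure is rare or other errors are common, and larger when other errors are rare. All of this rests on assumed rates, equal performance and independence.

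Two stronger readings should be resisted. One is that the primary result is biased: the item is non-critical as printed, and neither the endpoint nor N = 114 depends on it. The other is that the plan is definitely in breach of its own rule: that cannot be said until the misaligned table has been compared with the source form.

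**What to change.** 1. Compare Appendix 3 with the source checklist or eCRF. Confirm whether an ELLIPTA closing row exists, and that BREEZHALER step 12 can be ticked and is non-critical.
2. If the ELLIPTA row is absent, add a non-critical row for not closing the inhaler at step 3. Alternatively, state in the SAP that final closing is left out of the overall-error and need-for-instruction derivations for both devices.
3. If data are already collected, repeat the overall-error and need-for-instruction analyses without BREEZHALER step 12. The training times can be only partly repaired. A participant whose sole Attempt 1 error was step 12 can be treated as correct at T1 with T2 = 0. Later attempts would need a separate time for each attempt, which the schedule of activities does not list.

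The cost is one extra row or one extra analysis. The ELLIPTA overall-error rate may look slightly higher. In return, any ELLIPTA advantage on these endpoints could not be put down to this item.
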